11.6. Audits and Inspections

The investigational site may also be subject to quality assurance audits by DND*i* or designated representatives, and/or to inspection by regulatory authorities or IEC members.

The purpose of the inspections is to verify adherence to the protocol and to ensure the study is being conducted in accordance with Good Clinical Practice. It is important that the Investigators and the personnel concerned are available for any audits or inspections.

11.7. Data Management

An e-CRF must be completed for each patient who gives informed consent to participate in the study. A validated e-CRF will be used in the study. The study data will be stored in a computer database that ensures confidentiality of the data, in accordance with national legislation on data protection.

All data are entered in the e-CRF under the responsibility of the Investigator or a designated qualified staff member. The Investigator will provide a written document at the start of the study attesting that his/her electronic signature is equivalent to his/her written signature from a legal standpoint.

Data will be checked regularly by the clinical monitor. Data queries will be generated, documented and resolved on a regular basis throughout the study.

11.8. Confidentiality of Information, Study Documents and Patients' Files

The Investigator will ensure that the anonymity of patients is maintained and that their identity is protected from unauthorised third parties. Patients must not be identified by their names in the e-CRF or on any other documents submitted to the Sponsor. Only the patient number should appear. The Investigator must keep a patient enrolment log containing the number, name and address of patients. The Investigator must ensure the confidentiality of all documents submitted to the Sponsor's authorised representatives, including the signed informed form.

The findings of any assessments, including laboratory tests, will remain strictly confidential to the patient him/herself. This includes patients under legal age and vulnerable patients. Particular attention will be paid to the confidentiality of the results of pregnancy tests and tests related to concomitant diseases.

12. Protocol Amendments

The Investigators will ensure that the study is conducted in strict compliance with the protocol, and that all data are collected and recorded in the e-CRF.

All protocol modifications must be documented in writing. A protocol amendment can be initiated by either the Sponsor or any Investigator. The Investigator will provide the reasons for the proposed amendment in writing and will discuss it with the Sponsor and the Principal Investigator.

Any protocol amendment must be approved and signed by the Sponsor and the Principal Investigator, and must be submitted to the appropriate IEC for information and approval in accordance with local requirements, and to regulatory agencies, if required. Approval must be received from the IEC, and the regulatory authorities, if applicable, before any changes can be implemented, with the exception of changes required to avert an immediate risk for study participants, or when the change involves only logistical or administrative aspects of the study, e.g. changes in telephone numbers.

13. Early Termination of the Study

Both the Sponsor and the Principal Investigator will have the right to terminate the study early, i.e. at any time prior to inclusion of the planned number of patients, but they may exercise this right only for valid scientific or administrative reasons. If this is necessary, the two parties will define the procedures for terminating the study after consultation. The Sponsor and the Principal Investigator will ensure that early termination of the study takes place in such a way as to protect of the patients' interests.

Reasons for which the study may be terminated by the Sponsor include, but are not limited to:

- insufficient enrolment rate,
- protocol violations,
- inaccurate or incomplete data,
- dangerous or unethical practices,
- on recommendation from the DSMB or IEC.

Reasons for which the study may be terminated by the Investigator include, but are not limited to:

- insufficient time or resources to conduct the study,
- lack of eligible patients.

If the study is terminated early by the Sponsor or the Investigator, the latter must:

• complete all e-CRFs to the largest extent possible,

- return all study-related articles and equipment to the Sponsor who provided them,
- answer all queries from the Sponsor, or delegated representatives, related to data on patients enrolled by the site prior to study termination,
- ensure that patients enrolled in the study who have not yet attended any follow-up visits receive all necessary medical care,
- provide the IEC, the regulatory authorities and, if appropriate, the Sponsor with a written explanation of the decision to terminate the study.

14. Ethical Considerations

The protocol for this study was prepared in accordance with the general ethical principles set out in the Declaration of Helsinki of the World Medical Association (see Appendix 1 – Declaration of Helsinki; p 90) and ICH guidelines for Good Clinical Practice (ICH Harmonised Tripartite Guideline - Guideline For Good Clinical Practice E6(R1) - current step 4 version, dated 10 June 1996). DNDi commits to respect all applicable laws for the protection of the rights and welfare of human subjects.

The study was submitted to a panel of international experts who were invited, by the WHO, to provide an opinion on ethical aspects of the study, under the supervision of the French and Francophone Society for Medical Ethics (SFFEM) presided by [name]. The minutes of this meeting, as well as the responses from the Sponsor, are presented in appendix to the dossier for submission of the protocol to the various IECs.

The protocol will also be submitted by the National Investigator for official approval from the IEC in each country:

- the Ethics Committee of the Ministry of Health in the DRC,
- the Scientific Committee in charge of validating study protocols and results at the University of Bangui (Faculty of Health Sciences) in the CAR.

In addition, the protocol will be reviewed by the MSF Ethics Review Board prior to study initiation, since MSF is involved in the study as an implementation partner.

Formal approval must be obtained in each country prior to undertaking any protocol-specific procedure in any patient in the country concerned.

Any modification made to the protocol after receipt of the IEC approval must also be submitted in writing by the National Investigator to the IEC, in accordance with local procedures and regulatory requirements (see Section 12 Protocol Amendments; p 76).

The protocol will be submitted along with appendices relevant to the information and safety of patients, such as the patient information sheet & consent/assent form, and the Investigator Brochure. The set of images provided to the Investigators as visual aids to explain the study procedures will be presented to the IEC. The patient information sheet and consent/assent form should be formally agreed upon by each IEC separately. If necessary, during the protocol review process, the specificities of each country may be incorporated in a specific version of the protocol for the countries concerned.

14.1. Information of Communities14.1.1. Democratic Republic of the Congo

The Primary Investigator for the study is the Head of the National HAT Control Programme (PNLHAT) in the DRC. The programme is responsible for all prevention and treatment activities regarding HAT within the country, and in particular for the supervision and coordination of the mobile teams in charge of HAT screening activities. PNLTHA is fully involved in the design and implementation of the fexinidazole study in the DRC.

Information of the communities participating in the study will be provided at three different levels.

Firstly, the study will be presented to the public health representatives of the provinces concerned, namely the Provincial Medical Inspectors (*Médecins Inspecteurs Provinciaux*) and District Medical Officers (*Médecins Chefs de Zones*), as well as the District Administrators prior to any study-related activity in their respective geographic area of responsibility. Information on the study will be provided by the Provincial Coordinators of the PNLTHA (*Médecins Coordinateurs*), if possible in conjunction with a DNDi representative. The information will be based on the study protocol summary, the patient information sheet and consent form, and a summary of the Investigator Brochure.

Secondly, and before starting screening activities for the study in a given area or health zone, an adequate, HAT-experienced person with good knowledge of the area and local culture and good communication skills, i.e. either a member of a mobile team and/or a community mobiliser, will visit the local authorities, and tribal or village chiefs a few days before arrival of the mobile team, and inform them about the study and the related activities. In agreement with the local chiefs, an additional information session for the local population may be held, possibly during the usual community information session, which routinely takes place just before the start of screening activities by mobile teams. HAT is endemic in the regions where the study is to be conducted, and therefore, individuals already have a basic knowledge of the disease. In addition, most of the community mobilisers and many mobile team members have undergone specific training in community communication and HAT and will also receive additional study-specific training. Their experience and knowledge will therefore be highly useful in promoting a good understanding of the study.

The following information on the study will be disseminated at the community level:

- Routine procedures for detection and diagnosis of HAT;
- Primary objective of the study, i.e. to develop a safe oral drug to treat HAT that will be made available to the local population;
- Information on the new drug, the reference treatment as an alternative outside the study, the availability of a rescue treatment and on concomitant treatments as needed;
- Information on the duration of hospitalisation, number of follow-up visits up to 18 months as compared to routine treatment, importance of attending follow-up visits and possibility of visits by study staff at village level if the patient does not attend the follow-up visits at the centre;
- Information on provision of food to all HAT patients treated at the sites, regardless of whether they are included in the study;
- Information on organisation of transport and/or reimbursement of transport costs for patients included in the study;
- Importance of the freedom of each individual to accept or to refuse to take part in the study, after full explanation of the study. Availability of treatment in either case;
- Need for minors and patients with impaired cognitive capacities to come to the centre accompanied by a legal guardian/representative.

The third level of information concerns the individual consent of each patient (see Section 14.2. Informed Consent Process; p **Error! Bookmark not defined.**).

At the end of the study, the community will receive information on the results using the same means of communication, i.e. community mobilisers.

14.1.2. Central African Republic

In the CAR, a similar three-level approach will be used for communication and dissemination of information concerning the study on fexinidazole.

MSF Spain, in its role as operational partner for the study, will select a representative and/or ask the National or Local Investigator to inform the administrative and medical authorities in the district. The PNLHAT in the CAR is fully involved in the design and implementation of the fexinidazole study in the CAR, through its Coordinator, who is acting as National Investigator.

Contrary to the DRC, in the CAR there are no mobile teams specialised in HAT screening in the vicinity of the investigational centre chosen for the study, in Batangafo. Members of the laboratory staff of the hospital will be sent out to actively search for cases. The composition of the mobile teams is, however, the same as in DRC, with community mobilisers and other qualified personnel who are responsible for raising awareness of HAT among tribal chiefs, religious leaders, local authorities and the population.

Information sessions will be organised in public places, such as churches, mosques and markets, a few days before the start of screening activities, to sensitise the population to the advantages of screening. The overall objective of the study will be presented along with information on the study, as described above in Section 14.1.1 concerning the DRC.

The screening activities will receive funding from the Sponsor throughout the duration of the study. The activities will be organised by MSF Spain in Batangafo.

14.2. Informed Consent Process 14.2.1. General Process

The patient will not be included in the study until after s/he has given informed consent in writing. It is the responsibility of the Investigator to obtain, for each individual who participates in the study, voluntary written informed consent after having provided adequate explanation of the aims, methods, anticipated benefits, and potential hazards of the study. This task can be performed by a designee, referred to below as a "facilitator", who may be a study nurse.

The written informed consent document will be translated into the local language or a language understood by the patients, and submitted to the IEC in each country for approval.

A written guide, more extensive than the patient information, will be used as a tool for the facilitator to provide oral explanations. The facilitator will be chosen within the team for her/his good knowledge of the patients' preferred local language, and for his/her skills in interacting with patients. More than one facilitator may be chosen in each centre to cover all local languages and dialects.

Visual aids, including photographs, drawings and samples, will also be made available to the facilitator, describing the activities performed during the study, i.e. lumbar puncture, finger pricks, ECG, etc., and will be submitted to the IEC for approval.

The patient will be invited to attend the information session alone or together with family or friends if s/he wishes. The session will be held in a separate room in order to ensure patient confidentiality, with only one facilitator present.

The patient will first be informed about the disease, i.e. HAT, with a clear description of the signs and symptoms.

The information provided during the session will address the following topics:

- currently available treatments;
- study objective and need for scientific evaluation of a new drug;
- information on the new drug from previous studies (efficacy, safety...);
- number of patients to be enrolled and the duration of the study;
- criteria to fulfil to be eligible for inclusion in the study;

- patient's commitments during the study, i.e. time, compliance with studyspecific procedures and attendance at follow-up visits;
- samples to be collected for laboratory tests and purpose of tests;
- benefits and risks associated with study participation, for both treatment groups;
- compensation for travel costs and provision of food during hospitalisation;
- patients' rights regarding withdrawal, rescue treatment, additional information, etc.

If the patient wishes, s/he will be given time to discuss the information received with members of his/her community or family before giving consent. Written consent will be given after the information session (or later) by signing the form, provided the facilitator is convinced that the patient has fully understood what was explained.

All informed consent forms have been translated into the following local/national languages/lingua franca spoken in the areas where the study is being conducted: Lingala, Kituba/Kikongo and Tshiluba. If the patient does not speak any of the national/local language/lingua franca and if pre-specified and authorized staff with knowledge the dialect/local language are present, an *ad hoc* oral translation may be acceptable. The oral translation will be supported by the use of the available visual aids. The document signed by the patient will be the form in the lingua franca of his/her country/region. The procedures for illiterate patients should apply. The oral translation should be documented on the signed consent form, i.e. the person who did the translation will indicate her/his name and the language/dialect used, and will sign the form.

14.2.2. Impartial Witness

The presence of an impartial witness is mandatory when illiterate patients are recruited and/or the legal representative is illiterate (see Section 14.2.2. Impartial Witness; p 81). Other situations may also require such a witness (see Section 14.2.3. Illiterate Patients; p 82 and Section 14.2.4. Patients Unable to Give Consent; p 82)

The witness should have no connection with the research team, and, whenever possible, should be chosen by the patient. The witness must be literate, i.e. able to read. If the patient does not know any appropriate witness, the team will propose someone from the hospital staff who is not working in the HAT clinical unit, or any literate person from the neighbourhood who is willing to act as a witness. The study team will take all necessary measures to prepare a list of possible witnesses before the start of the study and keep this list updated, in order to find a witness quickly, whenever necessary.

The witness will sign the consent form to attest to the completeness of the information given to the patient, and its compliance with the written information in the patient information sheet. The witness must be present throughout the entire information session.

The witness will confirm that the patient has freely given his/her informed consent to participate in the study.

14.2.3. Illiterate Patients

If the patient is illiterate, an impartial witness must be present throughout the information session.

The facilitator will explain the information contained in the written document to the patient and ask whether he/she gives his/her consent to participate. The patient's consent will be documented with his/her fingerprint on the form, and the witness will sign the form.

14.2.4. Patients Unable to Give Consent

On arrival at the investigational centre, some patients with late-stage HAT may already have impaired cognitive capacities or behavioural abnormalities that preclude them from giving free and informed consent.

Considering the frequency of such symptoms in HAT, exclusion of these patients could jeopardise the capacity to complete the study.

Consequently, for patients who present with symptom(s) of psychological or behavioural disturbances and/or with impaired mental status, such as memory, alertness, disorientation, etc., consent will be requested from an accompanying family member, acting as legal representative. It should be noted that patients with very advanced late-stage HAT will not be invited to participate in the study (see exclusion criteria).

As is the case with minors, the eventual non-consent of the patient will prevail if s/he refuses to participate in the study.

In addition, the consent process should be conducted in the presence of an impartial witness who will attest that the patient's will and best interests have been respected.

As soon as the patient has recovered his/her capacity to decide, s/he will be asked to confirm his/her desire to participate in the study, usually during the hospitalisation period, attested by the signature of an additional consent form.

14.2.5. Patients Under Legal Age

For patients under legal age, i.e. between 15 and 18 years old, considered as adolescents/young adults, the consent of one of their parents or another culturally acceptable, legal representative will be required in addition to their own personal assent. During field visits by the mobile team, adolescents/young adult patients will be advised to come to the study centre accompanied by a legal representative.

No specific patient information sheet or specific form will be used to collect assent from adolescents/young adults recruited to the study, since the data in the patient information sheet is considered to be understandable by both adolescents and adults.

The form will be signed by both the adolescent/young adult and his/her legal representative. If the patient or the legal representative is illiterate, a fingerprint should replace the signature. If the legal representative is illiterate, an impartial witness must attend the assent process and the consent process for the legal representative (see Section 14.2.2. Impartial Witness; p 81).

For young adults considered as emancipated because they are already married, the legal representative may be the husband or wife. If they are not married but are living on their own, they may be included with their own consent, provided an impartial witness is present during the consent process to confirm their understanding of the study, to confirm the probability that they are indeed emancipated, and to sign the consent form along with them.

14.2.6. Changes in the Benefit-to-Risk Assessment during the Study

If new safety information results in significant changes in the benefit-to-risk ratio, the patient information sheet and consent form will be reviewed and updated. Patients currently being treated will be informed of the new information, given a copy of the revised patient information and asked to renew their consent to continue the study.

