18 months and 24	18 months ± 4 weeks 24 months ± 4 weeks	 Patient alive with no evidence of trypanosomes in any bodily fluid and CSF WBC ≤ 20/µL Patients with no signs of HAT and refusing to undergo 	 Any reason prompting the Investigator to request an additional follow-up visit 	 CSF WBC > 20/µL Neurological signs or symptoms leading to use of rescue treatment 	 Evidence of trypanosomes in any bodily fluid
24 months		lumbar puncture and who, in the opinion of the Investigator do not require rescue treatment or an additional follow-up visit			

An uncertain outcome may be a discrepancy between the clinical picture and the laboratory findings, or any situation that leads the Investigator and the study team to consider that an additional follow-up visit is required to decide whether or not to provide rescue treatment. This classification will not be used directly for statistical purposes.

6. Schedule of Study Procedures and Assessments6.1. Timing of Assessments

See Table 4 - Timing of Assessments (p 99)

- D-15 to D-1: Patient screening with detection of *T.b. gambiense*, pretreatment of concomitant malaria and/or helminthiasis, if any, ECG and laboratory screening tests
- D-4 to D-1: Baseline assessment
- D1 to D10: Treatment period
- D8 to D12: PK sampling for patients in the fexinidazole group
- D11: End-of-Treatment (EOT) visit
- between D13 and D18: End-of-Hospitalisation (EOH) visit; if hospitalisation is prolonged beyond D18, the EOH visit should be recorded on D18 and an unscheduled visit should take place at the actual time of discharge from hospital
- Additional Follow-up Visit: in Week 9 after D1, i.e. D64 to D70, for patients who reach this visit starting in mid-December 2014
- Follow-up Visits: at M3, M6, M12, M18 and M24 after D11, see Table 3 Theoretical Schedule of Visits and Acceptable Leeway). The timing of follow-up visits is calculated from D11 (EOT).

Theoretical schedule of visits	Ideal timing of visits	Acceptable leeway*	
End-of-Treatment visit (EOT)	D11 after the Start of Treatment (SOT) (D1 after EOT)	Between D11 and D12 after SOT (D1 or D2 after EOT)	
End-of-Hospitalisation visit (EOH)	Between D13 and D18 after SOT (D3 and D8 after EOT)	D18 at the latest	
Week 9 after D1	D64 to D70		
3 months	3 months ± 1 week after EOT	2-4 months after EOT	
6 months	6 months ± 2 weeks after EOT	5-9 months after EOT	
12 months	12 months ± 4 weeks after EOT	10-16 months after EOT	
18 months	18 months ± 4 weeks after EOT	17-21 months after EOT	

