6.3.3. Laboratory Tests

A repeat urine pregnancy test will be performed at discharge, i.e. between D13 and D18.

Blood haematology and biochemistry assessments will be repeated on D5, D8 and D11 (EOT visit). Safety biochemistry and haematology assessments will be performed 9 weeks after intake of the first dose on D1, only in patients who reach this visit from mid-December 2014 onwards. Blood samples will be analysed in the laboratory in each centre using standard equipment specifically provided for the study by the Sponsor. Whenever possible, the samples should be collected from patients in the fasting state.

Parasitology testing requires 5 mL of whole venous blood or 4 mL of CSF. The blood sample should be analysed on an mAECT column within 30 minutes after collection. The CSF sample should be examined after MSC within 15 minutes after collection. The WBC in the CSF sample should be performed within 15 minutes after collection. It is necessary to collect 5 mL of CSF to perform the two tests.

Full haematological and biochemistry analyses require at least 0.5 mL of capillary or venous blood. Capillary blood collection considerably reduces the total quantity of blood collected as compared to classical techniques. However, because it is not always feasible, collection of venous blood is permitted. Each sample corresponds to 2 mL per tube, one tube containing EDTA for Haematology and one tube containing heparin lithium for Biochemistry.

The urine analyses performed at screening, at the baseline assessment and at the EOT visit, as well as on D18 and at 3 months for female patients, require only a few millilitres (5-10 mL).

During hospitalisation, additional safety assessments such as haematology, biochemistry or urine tests may be performed at the discretion of the Investigator in order to monitor for abnormalities.

The volume and the number of samples required for each patient are presented by visit in Appendix 3 – Laboratory Assessments (p 96).

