6.5.9. Follow-up on AEs

All AEs must be followed until resolution, or until the Investigator considers them to be "chronic" or "stable", or until the patient's participation in the study ends, i.e. until the final report is completed for the study in which the patient was participating.

If the AE is a laboratory abnormality with a toxicity grade \geq 3, the test must be repeated 2 to 4 days later, and then at regular intervals until the parameter reaches toxicity grade \leq 1, or until it returns to the baseline level (see Baseline Assessment).

In addition, all SAEs and all events that the Investigator (and the Coordinating Investigator or the monitor, as needed) considers as possibly related to the study treatment must continue to be followed even after the end of the patient's participation in the study. Such events should be followed until their resolution, or until the Investigator considers them as "chronic" or "stable." The resolution of such events must be documented in the e-CRF, and if they are SAEs, on an SAE follow-up form.

7. Study Duration

The enrolment period is expected to last 18-20 months (see Table 7 – Expected Enrolment Rate; p 104). The duration of treatment will be 10 days in both treatment groups.

Each patient's participation will last approximately 25 months and will include:

- pre-treatment period (pre-screening and screening, treatment of concurrent disease)
- treatment period of 10 days
- hospitalisation for 3 to 8 days after treatment
- out-patient follow-up for 18 months, until the TOC visit

• additional follow-up for 6 months, until M24

The total duration of the study, including the preparative phase, is expected to be 48 months.

8. Withdrawal Criteria

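### Section 14.2.6 limits re-information and renewed consent to patients on treatment, which read literally leaves out everyone in follow-up

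*Protocol*

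**What the plan says.** Section 14.2.6 sets the trigger: "If new safety information results in significant changes in the benefit-to-risk ratio, the patient information sheet and consent form will be reviewed and updated". It then names the patients who are to receive the new information: "Patients currently being treated will be informed of the new information, given a copy of the revised patient information and asked to renew their consent". The sentence ends by describing this as consent to go on in the study.

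Elsewhere the protocol uses treatment in a narrow sense. Section 6.1 lists "D1 to D10: Treatment period". Section 7 says "The duration of treatment will be 10 days in both treatment groups" and, of the whole commitment, "Each patient's participation will last approximately 25 months and will include" a pre-treatment period, the treatment period, 3 to 8 days in hospital after it, "out-patient follow-up for 18 months, until the TOC visit" and "additional follow-up for 6 months, until M24".

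During follow-up, section 6.4.3 plans CSF sampling at 6, 12 and 18 months, and section 6.5.4 collects serious adverse events to 24 months.

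**The concern.** The group named in 14.2.6 is much smaller than the group to whom a benefit-risk change would matter. A patient who has finished the ten-day course has been exposed to the drug, is still being asked for lumbar punctures and follow-up visits, and may withdraw. Whether to continue is therefore a live decision for that patient, and 14.2.6 is the provision meant to support it.

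A site that follows the sentence as written would give the revised sheet to the few patients then on treatment and would have no instruction for the rest. What is at stake is patient protection and consistent practice across sites, not the statistical analysis.

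**Working it through.** **1. The plan's own figure.** Section 7 gives about 25 months. The inputs are screening of up to 15 days (D-15 to D-1), treatment of 10 days, and follow-up of 24 months from the end of treatment. At 30.44 days per month, (15 + 10) / 30.44 + 24 = 24.8 months, so the stated figure is reproduced.

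**2. Share of participation covered by the clause.**
- Of the whole participation: 10 / (25 × 30.4) = 10 / 760 = 1.3%.
- If being treated is stretched to mean D1 to D18, the latest routine discharge day (section 6.1): 18 / 760 = 2.4%.
- Counted from D1 with 24 months of follow-up (10 + 730.5 = 740.5 days): 10 / 740.5 = 1.4% for treatment and 18 / 740.5 = 2.4% for the hospital stay.
- Counted from D1 with follow-up only to the 18-month visit (10 + 547.9 = 557.9 days): 10 / 557.9 = 1.8% and 18 / 557.9 = 3.2%.

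On the most generous of these, 100 − 3.2 = 96.8% of the time after D1 lies outside the clause.

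**3. Patients covered on a given day.** This needs an assumption: even enrolment of the 390 patients, ignoring deaths and losses. The documents give several enrolment durations: 18 to 20 months in section 7, 24 months in Table 6, and about 30 months from the first visit in October 2012 (Table 6) to the last planned enrolments in the first quarter of 2015 (Table 7).
- Over 18 months: 390 / 18 = 21.7 per month, and 21.7 × 10 / 30.44 = 7.1 patients on treatment.
- Over 30 months: 390 / 30 = 13.0 per month, and 13.0 × 10 / 30.44 = 4.3 patients on treatment.
- In follow-up when enrolment ends: between 13.0 × 18 = 234 (30-month enrolment, 18-month follow-up) and all 390 (18-month enrolment).

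**4. Calendar.** Table 6 puts the last 18-month visit in September 2016. Eighteen months earlier is March 2015, which agrees with Table 7. The last 24-month visit is in March 2017. From about March 2015 nobody is on treatment, so for the last 18 months (to the primary endpoint) or 24 months (to the end of follow-up) the clause, read literally, applies to no patient.

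**5. Does another passage fill the gap?**
- Section 14.2.1 lists a right to additional information among the topics of the initial session. It sets no duty to re-inform or re-consent.
- Section 14.2.4 asks for a further consent only from patients who regain the capacity to decide.
- Section 14.1.1 returns results to the community at the end of the study.
- Section 14.4 distinguishes the in-patient treatment phase from follow-up visits, which supports the narrow reading of treatment.

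None of these extends 14.2.6 to patients in follow-up.

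**The case against.** **Loose wording.** The sentence closes by speaking of consent to go on in the study. For a ten-day course within 25 months, that fits a writer who meant all current participants. This is a fair reading and probably the intended one, so the text does not show a decision to exclude follow-up patients. But it does not say that they are included either.

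**Other safeguards.** Section 14.2.6 does not forbid informing others. Section 14 has each ethics committee agree the information sheet and consent form and receive protocol changes, and section 10 has the steering committee advise if the benefit-risk balance is in jeopardy. The scope could be widened at that point. That softens the consequence, but it leaves the standing rule too narrow.

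**Routine follow-up.** Section 1.3 presents repeat lumbar puncture as needed to confirm cure, and a past exposure cannot be undone. Both points are true, but the patient's decision to continue or withdraw remains.

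Three stronger readings are tempting, and the documents do not support them.
- A reader might infer that follow-up patients would not know to return. Sections 6.4.5 and 6.5 already tell patients to come back whenever they feel unwell, whatever the suspected cause.
- A reader might infer that late serious adverse events would be under-reported and that endpoint weakened. Section 6.5.3 has patients questioned and examined for adverse events at every follow-up visit, section 8.4 requires efforts to contact those who miss visits, and nothing links the consent wording to ascertainment.
- A reader might take the added visit ("Safety biochemistry and haematology assessments will be performed 9 weeks after intake of the first dose on D1", for patients reaching it from mid-December 2014) as proof that late toxicity was expected. Neither section 6.1 nor 6.3.3 gives a reason for it.

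**Conclusion.** The point holds as a minor correction of consent scope. Read literally, 14.2.6 covers about 1.3% of roughly 25 months, or about 2 to 3% if the hospital stay is meant, and on the planned schedule it covers nobody after about the first quarter of 2015. The percentages rest only on the protocol's stated durations. The patient counts (about 4 to 7 on treatment on any day) also assume even enrolment without deaths or losses. The consequence arises only if a significant benefit-risk change occurs. Sample size, type I error and the analyses are unaffected.

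**What to change.** In section 14.2.6, replace the group now named with: *All patients still participating in the study, including those in follow-up to Month 24*. Add that they are informed and asked to renew consent at the next scheduled visit, or earlier if the information calls for it, through the village-level visits by study staff that section 14.1.1 already foresees for patients who do not attend.

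The cost is one sentence of amendment and, only if such a change occurs, a re-consent step at visits already scheduled.
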